3.3 Other Endpoints

Many of these proposed outcomes are not meant to definitively establish the underlying mechanisms, but instead will explore biochemical endpoints to provide additional support or generate other hypotheses of how the interventions may result in different clinical outcomes.

- 1. Increase of PaO₂ / FiO₂ ratio on study days 1-7
- 2. Improvement in Lung Injury Score on study days 1-7
- 3. Number of gastrointestinal intolerances (aspiration, vomiting, regurgitation, diarrhea, elevated gastric residual volumes, abdominal distention and cramping) on study days 1-7
- 4. Level of systemic inflammation, as measured by plasma IL-6 and IL-8 levels.

5.

- 6. Measure of oxidative stress on days 3, 6 and 12 compared to baseline as measured by urinary levels of F₂-isoprostane metabolites
- 7. Incidence of bacteremia.
- 8. Incidence of Clostridium dificile induced diarrhea.
- 9. Incidence of ventilator-associated pneumonia
- 10. Serum levels of markers of nutrition, including albumin and total protein levels between baseline and days 6 and 12.

Clostridium dificile diarrhea will be diagnosed by one or more daily stool specimen positive for cytotoxin assay or enzyme immunoassay. Patients with more than 3 liquid stools totaling more than an estimated 500 ml of stool per day, or those with systemic inflammatory response

syndrome unexplained by other infection, may have up to three daily stool samples sent for *C. difficile* investigation (either cytotoxin assay or enzyme immunoassay).

Bacteremia will only be considered if it develops greater than 24 hours after the initiation of study procedures and is documented with a positive blood culture. The primary medical team, using clinical judgment, will determine when blood cultures are sent. Coagulase negative (or thermo nuclease negative) *Staphylococci* or *Corynebacterium* bacteremia require the isolation of these organisms from at least two blood cultures drawn within 24 hours of each other containing the same organism in order to be deemed significant.

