9.2 Risks of Full-calorie Enteral Feedings

Potential common risks to patients in the early full-calorie feeding group are more episodes of gastrointestinal intolerance of the tube feedings. GI intolerance includes abdominal distention, abdominal cramping, nausea, vomiting and diarrhea. GI intolerance could lead to more vomiting and aspiration. The early full-calorie feeding group may also experience more diarrhea. Additionally, patients receiving early full-calorie enteral feeds may be at an increased risk for intestinal ischemia or infarction. Because they will receive more calories, patients in this group may be at risk of having higher blood glucoses. The treatment of the higher blood glucoses will be standardized to help control for this confounder, which will likely precipitate the full-calorie feeding group receiving more insulin. The clinical significance of additional insulin is uncertain. Early full-calorie feedings could theoretically reduce the risk of infection by improving nutritional status, but could also be associated with increased infection risk from hyperglycemia or aspiration pneumonia.

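### Section 3.3 scores C. difficile-induced diarrhea from any one positive stool test, so a positive without diarrhea, or an infection present before randomization, can count as a new case

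*Protocol*

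**What the plan says.** Item 8 of Section 3.3 (Other Endpoints) is "Incidence of Clostridium dificile induced diarrhea". The case definition below the list reads: "Clostridium dificile diarrhea will be diagnosed by one or more daily stool specimen positive for cytotoxin assay or enzyme immunoassay".

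The Protocol then says who may be tested. The first trigger is stool output: "Patients with more than 3 liquid stools totaling more than an estimated 500 ml of stool per day". The second, an alternative to the first, is a systemic inflammatory response that no other infection accounts for; it does not mention stool. Under either trigger testing is permitted rather than required, with at most three daily samples.

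The neighbouring bacteremia definition has an onset rule: "Bacteremia will only be considered if it develops greater than 24 hours after the initiation of study procedures".

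On diarrhea itself, Section 5.1.7.5 defines it with the same stool count and volume as the first trigger. Section 2.4 hypothesizes fewer gastrointestinal intolerances, diarrhea among them, with trophic feeding. Section 9.2 says "The early full-calorie feeding group may also experience more diarrhea".

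Appendix E leaves day 0 blank for C. difficile tests and records them, when available, on days 1 to 12 and day 14. It records gastrointestinal intolerances on days 1 to 12 only.

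**The concern.** The endpoint's name describes diarrhea caused by C. difficile and arising during the trial. The rule that decides a case asks only for a positive test. Two kinds of patient can be misclassified:

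- a patient tested for an unexplained inflammatory response who has no diarrhea;
- a patient already infected or colonized at randomization who is first tested on study.

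A further issue is ascertainment. A patient can become a case only if stool is sent. One of the two reasons for sending it is an outcome on which the arms may differ, and the staff who send it know the feeding assignment. If the arms were tested to different extents, part of any difference in recorded incidence would come from testing. It could then be read as an infectious effect of the feeding strategy.

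**Working it through.** The Protocol states no rate, power or detectable difference for this endpoint, so there is no figure to reproduce. The check is mainly a comparison of texts.

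**1. Is diarrhea required?** The diagnostic sentence names only the assay result. A sample sent under the first trigger comes from a patient who meets the diarrhea definition. A sample sent under the second need not. Followed as written, the rule scores a positive from the second route as diarrhea. The gap is therefore limited to that route and to samples sent outside the stated criteria.

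**2. Is new onset required?** The C. difficile definition has no onset rule; bacteremia has the 24-hour rule. Appendix E collects no day 0 test. This keeps tests from before day 1 out of the record, but it limits when a result is entered and not when infection began. With no baseline test and no lag, a prevalent infection tested on day 1 or later cannot be told from a new one.

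**3. Can testing affect the comparison?** Let q be the toxin-positive prevalence, set equal in both arms so that there is no true effect, and let t be the fraction tested. Then

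recorded incidence = q × t

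recorded ratio = (q × t_full) / (q × t_trophic) = t_full / t_trophic.

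The prevalence cancels, so the spurious ratio is simply the ratio of the tested fractions. The documents give neither q nor t. The values below are assumptions that show the range. They use about 500 patients per arm (Section 4.1) and a two-sided comparison of proportions at 0.05.

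| Tested, trophic vs full-calorie | q | Recorded incidence | Ratio | Chance of nominal p < 0.05 |
|---|---|---|---|---|
| 20% vs 20% | any | equal | 1.00 | 5% |
| 20% vs 25% | 5% | 1.0% vs 1.25% | 1.25 | about 6% |
| 20% vs 25% | 10% | 2.0% vs 2.5% | 1.25 | about 8% |
| 20% vs 25% | 20% | 4.0% vs 5.0% | 1.25 | about 12% |
| 20% vs 30% | 5% | 1.0% vs 1.5% | 1.50 | about 11% |
| 20% vs 30% | 10% | 2.0% vs 3.0% | 1.50 | about 17% |
| 20% vs 30% | 20% | 4.0% vs 6.0% | 1.50 | about 31% |

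At q = 5% with 20% vs 30% tested, the expected counts are 500 × 0.010 = 5 and 500 × 0.015 = 7.5. The chances in the last column are approximate at counts this small. The table shows how the mechanism works. It does not estimate what will happen in this trial.

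**The case against.** The strongest reply is that the endpoint's name, and Section 6.3, which collects episodes under that same name, already imply diarrhea, and that Appendix E starts recording on day 1. Both points narrow the gap. Patients tested by the first trigger do have diarrhea, and tests before day 1 are not collected. Neither closes it: the operative sentence still turns a positive without diarrhea into a case, and a prevalent infection tested later is still counted as new.

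A reader might go further and infer that the full-calorie arm will be tested more often, so that the endpoint is biased against it by a known amount. The documents do not support that:

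- Section 9.2 says only that this arm may have more diarrhea.
- Section 5.1.7.5 says diarrhea seldom has enteral feeds as its only cause.
- Testing is optional under either trigger.
- Section 9.3 says trophic feeding could impair control of infections, which could push the inflammatory-response trigger the other way.
- Any ratio quoted is just the assumed testing fractions divided, and equal testing gives 1.0.
- If C. difficile causes some of the extra diarrhea, part of a difference would be real.

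It is also fair to say that clinically triggered ascertainment is used elsewhere in Section 3.3, since blood cultures are sent on the primary team's judgment. This endpoint has no hypothesis in Section 2.4, no entry in Table 3 and no role in the stopping rules. That fixes its weight as low. It does not make the stated rule match the endpoint's name.

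**Conclusion.** The definition in Section 3.3 misclassifies in two specific ways: it counts positives without diarrhea as diarrhea, and it counts infections present at randomization as incident. Both follow from the text and need no outside assumption, though how many patients would be affected cannot be derived from the documents.

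Differential testing is a possible contributor to an arm difference and should be carried as a caveat, not as a demonstrated bias. It rests on the Protocol's expectation about diarrhea, on permissive testing and on unblinded feeding. Section 3.3 itself cites the unblinded feeding as a reason for an objective pneumonia definition. Its size is unknown because no testing or carriage rates are given, and it is nil if the arms are tested equally.

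This is an exploratory endpoint, and ventilator-free days and mortality are unaffected. The point is minor but cheap to correct.

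**What to change.** Amend the definition in Section 3.3 so that an incident case requires all of the following:

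- a positive specimen collected more than 24 hours after study procedures begin, matching the bacteremia rule;
- no known earlier positive test;
- diarrhea meeting Section 5.1.7.5 accompanying that specimen.

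List positives without diarrhea separately.

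Report the number of patients and of samples tested in each arm beside the incidence. This last step is needed because the tighter case definition does not remove differential testing; it ties cases more closely to diarrhea. Only the testing counts let a reader judge how much of a difference could come from who was tested.

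The cost is a few lines of text and slightly fewer counted events. Test results and daily intolerances are already in Appendix E, and a known earlier positive can be taken from the chart. One item must be added: diarrhea status for day 14 positives, because intolerances are recorded only through day 12. The change concerns scoring and reporting only.

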4.1 Number/Source/Screening

The trial will accrue a maximum of 1000 patients over a 3-4 year interval. Approximately 500 patient will be randomized to initial trophic feeding and 500 to initial full calorie feeding. The first 272 patients were enrolled in a 2 x 2 factorial design with an Omega 3 Fatty acid rich medical food versus a control isocaloric medical food. This portion of the trial was stopped by the DSMB for futility.

Patients with ALI or ARDS will be recruited from intensive care units at NIH ARDS Network centers. Study coordinators will visit intensive care units daily to identify potential candidates for enrollment (see inclusion criteria, section 4.2, and exclusion criteria, section 4.3. Permission to approach patients and/or their families will be requested from the attending physicians. All patients meeting the inclusion criteria will be entered on a screening log. If the patient is not enrolled, the screening log will include information explaining why enrollment did not occur (exclusion criteria, attending physician denial, patient refusal, etc. see Appendix L).

4.2 Inclusion Criteria

Patients will be eligible for inclusion if they meet all of the below criteria. Criteria 1-3 must all be present within a 24-hour time period: Acute onset (defined below) of:

1. $PaO_2 / FiO_2 \le 300$ (intubated). If altitude > 1000m, then $PaO_2 / FiO_2 \le 300$ x (PB/760)

- 2. Bilateral infiltrates consistent with pulmonary edema on frontal chest radiograph. The infiltrates may be patchy, diffuse, homogeneous, or asymmetric
- 3. Requirement for positive pressure ventilation via endotracheal tube, and
- 4. No clinical evidence of left -sided cardiac failure to account for bilateral pulmonary infiltrates.
- 5. Intention of primary medical team to enterally feed the patient

The 48-hour enrollment time window begins when criteria 1-3 are met. If a patient meets the first three inclusion criteria but has a PAOP (Pulmonary Arterial Wedge Pressure) greater than 18 mmHg, then the first four criteria must persist for more than 12 hours after the PAOP has declined to \leq 18 mmHg, and still be within the 48-hour enrollment window.

"Acute onset" is defined as follows: the duration of the hypoxemia criterion (#1) and the chest radiograph criterion (#2) must be \leq 28 days at the time of randomization. Opacities considered "consistent with pulmonary edema" include any opacities not fully explained by mass, atelectasis, or effusion or opacities known to be chronic (greater than 28 days). Vascular redistribution, indistinct vessels, and indistinct heart borders alone are not considered "consistent with pulmonary edema" and thus would not count as qualifying opacities for this study.

4.3 Exclusion Criteria

- 1. Age younger than 13 years.
- 2. Greater than 48 hours all since inclusion criteria met
- 3. Neuromuscular disease that impairs ability to ventilate with out assistance, such as cervical spinal cord injury at level C5 or higher, amyotrophic lateral sclerosis, Guillain-Barré Syndrome, or myasthenia gravis (See Appendix B)
- 4. Pregnant or breast-feeding
- 5. Severe chronic respiratory disease (See Appendix B for detailed exclusion criteria).
- 6. Burns greater than 40% total body surface area
- 7. Malignancy or other irreversible disease or condition for which 6-month mortality is estimated to be greater than 50% (See Appendix B).
- 8. Allogeneic bone marrow transplant within the last 5 years
- 9. Patient, surrogate, or physician not committed to full support (Exception: a patient will not be excluded if he/she would receive all supportive care except for attempts at resuscitation from cardiac arrest).
- 10. Severe chronic liver disease (Child-Pugh Score of 11-15)
- 11. Diffuse alveolar hemorrhage from vasculitis.
- 12. Morbid obesity (> 1kg/cm body weight)
- 13. No consent/inability to obtain consent
- 14. Unwillingness or inability to utilize the ARDS network 6 ml / kg PBW ventilation protocol
- 15. Moribund patient not expected to survive 24 hours
- 16. No intent to obtain central venous access for monitoring intravascular pressures.

- 17. > 72 hours since mechanical ventilation initiated
- 18. Refractory shock (See Appendix B)
- 19. Unable to obtain enteral access
- 20. Presence of partial or complete mechanical bowel obstruction, or ischemia, or infarction
- 21. Current TPN use or intent to use TPN within 7 days
- 22. Severe malnutrition with BMI < 18.5 or loss of > 30% total body weight in the previous 6 months
- 23. Laparotomy expected within 7 days
- 24. Unable to raise head of bed 30-45 degrees
- 25. Short-bowel syndrome or absence of gastrointestinal tract
- 26. Presence of high-output (> 500 cc/day) enterocutaneous fistula
- 27. Allergy to enteral formula
- 28. Requirement for, or physician insistence on, enteral formula supplemented with omega-3 fatty acids (ex: Oxepa®, Impact®) or providing omega-3 fatty acid or GLA supplementation

4.4 Enrollment, Randomization, and Study Initiation Time Window

All patients must be randomized within 48 hours of meeting inclusion criteria for ALI (inclusion criteria 1-3) and within 72 hours of initiating mechanical ventilation. The window for randomization will begin at the time of meeting all inclusion criteria and/or the time of documentation of mechanical ventilation, regardless of hospital location. The first three inclusion criteria may be met at either the Network or referring hospital. Following randomization, the low tidal volume protocol for mechanical ventilation must be initiated within one hour (if not already being utilized). Enteral feeds and the enteral feeding protocol must be initiated within 6 hours of randomization.

4.5 Informed Consent

Informed consent will be obtained from each patient or surrogate prior to enrollment in the trial. No study procedures will be done prior to obtaining informed consent.

4.6 Randomization

After obtaining a signed and dated informed consent, the coordinating center will be called and an assignment, in the form of a study ID number, will be made by computer-generated randomization to initial trophic or initial full feedings.

Randomization will be accomplished with a web based randomization system. Each research coordinator will have a unique Personal Identification Number (PIN). The randomization will indicate to study personnel whether the patient is to receive initial trophic or initial full feedings.

The randomization will be stratified by institution, and by shock at study entry to one of the two study arms.

4.7 Minorities and Women and Children

Gender and racial patient subsets were considered by the NHLBI in selecting the Network Centers. The demographic profiles of the Centers selected for the Network show that the aggregate patient population contains representative proportions of minorities and women. Recruitment of minorities and women will be monitored by the Network Coordinating Center. If necessary, additional recruitment efforts will be made at specific centers to ensure that the aggregate patient sample contains appropriate gender and minority subsets.

Children will be enrolled who are 13 years and older. There is general agreement that children in this age range have pathophysiology and outcomes similar to adults with ALI. In addition the study procedures called for in the protocol can be readily carried out safely and effectively in this population.

5 Study Procedures

5.1 Enteral Feeding Procedures

5.1.1 Enteral Feeding Formula

Feedings in both groups will employ a sterile, commercially available standard enteral formula (not supplemented with n-3 fatty acids) used in the ICU. Any formula that does not contain supplemental n-3 fatty acids or anti-oxidants will be acceptable to use. Enteral formulas supplemented with n-3 fatty acids will not be allowed based upon the OMEGA study being stopped for futility. N-3 fatty acid supplementation will not be permitted during the study. The list of formulas that are not allowed includes: Oxepa®, Impact®, Peptamen AF®, Crucial®, Optimental® and Pivot 1.5®.

5.1.2 Enteral Feeding Site

The location and type of enteral feeding tube (nasogastric, nasoenteric, PEG, orogastric, oroenteric, etc.) will not be randomized, but will instead be determined by the patient's primary medical team. The location of the feeding will be documented on the case report form. Consideration should be made for advancing the feeding tube to a post-pyloric position in patients receiving gastric feeds who experience multiple elevated gastric residual volumes (see section 5.1.4) or vomiting (see section 5.1.7.4).

5.1.3 Enteral Feeding Rates

All patients will have enteral feeds started within 6 hours of being enrolled and randomized. Upon admission to the ICU, a full-calorie feeding rate should be determined. The full-calorie feeding rate will be calculated to deliver 25-35 kcal/kg PBW each day (Cerra, 1997). If a formal dietary evaluation is done, the dietary recommendation can be used as an acceptable alternative full-calorie rate.

The following formulas will be utilized to calculate predicted body weight (PBW):

For males: PBW (kg) = 50 + 2.3 [height (*inches*) - 60] = 50 + .91 (height (*cm*) - 152.4) For females: PBW (kg) = 45.5 + 2.3 [height (*inches*) - 60] = 45.5 + .91 (height (*cm*) - 152.4)

5.1.3.1 Trophic Enteral Feeding Treatment Group (Trophic Feeding Group)

All patients randomized to trophic enteral feedings will have enteral feeds started at 20 kcal / hr and continued at this rate for 144 hours (see Trophic Feeding Protocol, Appendix C) provided gastric residuals remain at an acceptable level (see Gastric Residuals, section 5.1.4) and provided the patient remains on the ventilator. Thus, patients in the trophic feeding arm will receive 480 kcal, which is approximately 25% of total caloric goals each day. This caloric delivery lies within the range of data from published studies in animals and neonatal humans (Burrin, 2000; McClure, 2000; Ohta, 2003; Omura, 2000; Owens, 2002; Tyson, 2005). After 144 hours of trophic enteral feeds, the feeding rate will be advanced to full-calorie rates using the same protocol as for the full-calorie feeding treatment group (see section 5.1.3.2 and Appendix D) provided the patient remains on the ventilator.

5.1.3.2 Full-calorie Enteral Feeding Treatment Group (Full-calorie Feeding Group)

The full-calorie feeding group will have enteral feeds initiated at 25 cc / hr. If gastric residuals remain at an acceptable level (see Gastric Residuals, section 5.1.4), the feeding rate will be increased by 25 cc / hr every 6 hours until goal rate (as determined by the dietary evaluation if available) is achieved (see Full-calorie Feeding Protocol, Appendix D). This pattern of advancement is similar to advancement rates used in other feeding trials (Adam, 1997; Rice, 2005).

5.1.4 Gastric Residuals

The gastric residual volume (GRV) will be the amount of gastric contents able to be withdrawn from the gastric tube using a 60 cc syringe. If gastric residuals exceed 400 cc (McClave, 2002), the feeding rate will be adjusted according to the full-calorie feeding protocol (see Appendix D). If the patient has a post-pyloric feeding tube, gastric residuals will be measured only if a separate gastric port on the feeding tube or a separate gastric tube is in place. GRV in patients receiving post-pyloric feeding will only be considered significant if they exceed 400 cc and contain tube feeding formula. The aspiration of gastric juice in patients fed through post-pyloric tubes will not be considered gastric residual for the purpose of adjusting tube feeding rates unless it contains enteral formula.

Since a single, isolated, elevated gastric residual has been shown to be a poor predictor of enteral feeding tolerance (Mentec, 2001; Spain, 1999), enteral feeding rates will not be adjusted after a single elevated gastric residual. However, enteral feeding rates will be decreased or held if two or more GRVs are elevated (see Appendix D) as this likely represents impaired gastrointestinal tolerance of enteral feeding (Mentec, 2001; Spain, 1999).

The use of pro-kinetic agents and/or advancing the distal location of the feeding tube to a post-pyloric position should be considered in patients experiencing more than one episode of elevated gastric residual volume.

5.1.4.1 Gastric Residuals -Trophic Feeding Group

GRVs will be checked every 12 hours while patients are receiving trophic feeding rates. If GRV remains less than or equal to 400 cc, GRV will be replaced and tube feeds will continue at 20 kcal / hr (see Appendix C). If GRV exceeds 400 cc, 400 cc of the residual volume will be replaced, tube feeds will continue at 20 kcal / hr and GRV will be rechecked in 2 hours. If GRV remains greater than 400 cc, tube feeds will be held. GRV will be replaced (up to 400 cc) and gastric residual rechecked every 2 hours. Tube feeds will continue to be held until residual volume is less than or equal to 400 cc. Once residual volume is less than or equal to 400 cc, trophic tube feeds will be restarted at a rate of 20 kcal / hr.

When the trophic feeding group is advanced to full-calorie enteral feeds (after 144 hours of trophic feeds), GRVs will be checked according to the full-calorie feeding protocol (see section 5.1.4.2 and Appendix D).

